Name of study: Assessing the use of electronic cigarettes (e-cigarettes) as a harm reduction strategy

Research Protocol**PURPOSE OF THE STUDY**

Electronic nicotine delivery devices often referred to as e-cigarettes, are battery-powered devices that deliver vaporized nicotine when inhaled. Corresponding with the growth in media attention, marketing and promotion, awareness and use of e-cigarettes has increased dramatically. A large proportion of those using e-cigarettes use them to reduce the number of cigarettes they are smoking or to help them quit. Use of an e-cigarette by smokers unwilling or unable to stop smoking completely might be a good approach to reducing cigarette consumption as the e-cigarette imitates some behavioral aspects of cigarette smoking and contains nicotine. Moreover, the few existing studies on the effect of e-cigarettes on tobacco withdrawal and craving suggest promising potential to assist smokers in coping with smoking urges and decreasing cigarette use. The purpose of this study is to examine the feasibility of using e-cigarettes as a method for harm reduction and the effects of providing e-cigarettes (or placebo e-cigarettes) on smoking outcomes.

BACKGROUND

Most smokers want to quit and have made multiple quit attempts but the majority fail due to their dependence on nicotine and behavioral cues that reinforce their smoking behavior (Buckhalter 2005). Nicotine replacement therapy (NRT) is one of the most cost-effective treatments available to smokers who want to quit, but fewer than 20% of people quitting with NRT patch are abstinent at 12 months (Ronckers 2005, Stead 2012). This may be due to the fact that the NRT patch does not replace the behavioral ritual associated with cigarette use, nor deliver nicotine as rapidly as cigarettes (Le Houezec 2003, Walker 2011). It has been hypothesized that e-cigarettes could be a more effective way to help people reduce the harm of smoking through reductions in number of cigarettes smoked per day or to quit smoking completely by addressing both nicotine and behavioral dependence (Bullen 2010). A related question is the extent to which any quitting assistance provided by e-cigarettes might be attributable simply to the behavioral replacement they provide (Caponnetto 2011). This is relevant because some e-cigarettes are available with cartridges containing as little as 0mg of nicotine.

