E-cigarette use appears to be growing and highest among young adults 18-24 years. A study conducted in Hawaii found that smokers who used e-cigarettes to try to quit were younger and had been smoking for fewer years than those who had not. Notably, the most recent analysis of trends in smoking in the US found that between 2005-2010 young adults had the lowest quit rates compared to other adult age groups (CDC 2014). These findings suggest a rationale for focusing on the young adult population in studying the potential use of e-cigarettes as a harm reduction strategy. There are an estimated 2.5 million e-cigarette users in the US with sales of \$300 million a year (McCauley 2012). Many of these users are turning to e-cigarettes as a way to reduce or stop smoking. More research is needed to assess the effect of e-cigarette use on withdrawal symptoms, and its association with smoking reduction and abstinence.

The rationale for this harm reduction pilot study is based upon prior work demonstrating that pre-cessation nicotine replacement therapy (NRT) has been shown to increase the odds of reducing consumption of cigarettes per day (CPD by 50% or more compared to placebo) (Stead 2010). This prior work is especially noteworthy because smokers not interested in quitting made significant reductions in their smoking and maintained these reductions over time. Concern that pre-cessation NRT use will result in fewer quit attempts and impede cessation has not been supported by the literature. Among 19 relevant studies, none showed that pre-cessation NRT undermined future cessation. On the contrary it

Name of study: Assessing the use of electronic cigarettes (e-cigarettes) as a harm reduction strategy

appears that pre-cessation NRT is associated with smoking reduction which in turn increases the probability of future cessation (Hughes 2006).

METHODS

Primary research questions:

- 1) Is it feasible to recruit and retain young adult smokers in a pilot trial testing whether e-cigarette use can reduce the number of cigarettes smoked per day (CPD)?
- 2) To what extent do smokers reduce CPD when using e-cigarettes to displace cigarette use?
- 3) Are there differences in rates of reduction between two interventions arms (4.5% vs. 0 mg (placebo) e-cigarettes)?

Study Aims

AIM 1: To evaluate the feasibility of recruiting and retaining young adult smokers in a harm reduction study using e-cigarettes to displace cigarette use;

[figure not shown]

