AIM 2: To assess daily patterns of e-cigarette use (including dual use of combustible cigarettes), product satisfaction, and nicotine cravings with use of 4.5% vs 0 mg (placebo) e-cigarette; and

AIM 3: To compare the effect of nicotine e-cigarettes (4.5%) vs placebo e-cigarettes on smoking reduction at 1, 3 and 12 weeks post baseline assessment.

Study design

This pilot study will be a two-arm, randomized controlled trial. We will randomize 50 participants into each intervention arm. Participants will be recruited through advertisements placed in Craigslist and other social media as well as flyers placement in NYU venues and street distribution with contact details for how to get in touch with a Research Assistant. The randomization sequence will be prepared by the study statistician. Participants will be randomized to one of the two arms: e-cigarettes with nicotine cartridges or e-cigarettes with placebo cartridges (0mg). Participants and research assistants will be blind to the allocation of nicotine or placebo e-cigarettes as there are no difference in appearance or odor of the mist emitted from the e-cigarettes with and without nicotine containing cartridges.

Figure 1. Study design

Study participants

Inclusion criteria: ages 21-35 (must present proof of age), daily smoker, smokes at least 10 cigarettes a day (verified by a CO level of 8 ppm or above), interested in reducing CPDs, able to provide consent, uses a cell phone and is willing/ able to receive and respond to daily text messages regarding his/her cigarette use and e-cigarette use on his/her cell phone, and willing to use an e-cigarette for 3 weeks.

Exclusion criteria: Pregnant and/or breastfeeding (self-reported), current use of smoking cessation medications (including other forms of NRT, bupropion, or varenicline), enrolled in a smoking cessation program or another cessation trial. Other exclusion criteria include use of an e-cigarette in the past 14 days, use of any other tobacco products (pipe, cigar, cigarillos, snuff, chewing tobacco, or hookah/shisha) in the past 30 days, an Alcohol Use Disorders Identification Test (AUDIT C) score of ≥ 7

Name of study: Assessing the use of electronic cigarettes (e-cigarettes) as a harm reduction strategy

for men and ≥ 5 for women, a Drug Abuse Screening Test-10 (DAST) score of ≥ 5 . Potential participants will also be excluded if they report having a history of asthma or other airways disease and heart disease.

Study Procedures

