After tracking their cigarette use, all participants will receive a 20-30 minute behavioral counseling consultation with a trained tobacco counselor. The counseling session will be scheduled at the baseline visit. Counselors will review each participant's smoking pattern from the three days of tracking and offer tailored behavioral and environmental change strategies including specific smoking reduction strategy options, such as eliminating cigarettes at work, in the home, or least favorite or most favorite cigarettes of the day, carrying only those cigarettes needed for that day, dropping cigarettes associated with less intense triggers first, avoiding smoking triggers, using oral or manual replacements, and other strategies to manage urges. Since there is inadequate evidence that any one of these strategies was more effective than another, participants will be encouraged to choose those that are most appealing. Goal setting, and barriers identification will be used to help participants improve confidence in their ability to reduce the number of cigarettes they smoked (Josephs 2008).

In Summary, the baseline visit includes 1) completion of baseline survey, 2) registering subject on text messaging program, 3) have subject practice using the text message program, 4) proactive using e-cigarette 5) make appointment for counseling session and for returning to pick up e-cigarettes.

Participants will be encouraged to reduce the number of cigarettes smoked daily to at least 50% of the total number of cigarettes smoked per day at baseline. This level was selected a priori as a clinically significant measure of reduction and to be a substantial enough reduction to address partial compensatory smoking (Glasgow 2009). Participants will be encouraged to substitute the use of the e-cigarettes for each cigarette they eliminate in order to reduce nicotine withdrawal symptoms.

After the counseling session, they will return to [name] to pick up their supply of disposable electronic cigarettes to last one week. They will be reimbursed for travel expenses. At the end of week

Name of study: Assessing the use of electronic cigarettes (e-cigarettes) as a harm reduction strategy

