We will send questions via text messages for a total of 24 days (3 days of baseline assessment of cigarette use and 21 days of dual use with e-cigarette). The first phase of data collection will include a three-day baseline assessment of the study participants' usual smoking pattern. This will begin the day after the baseline assessment. Participants will receive text messages approximately every 4 hours (4 times/day). The questions will only ask about cigarette use in the previous time period, mood and cravings (Table 2). We will wait until the study participant responds to the first message before sending each follow up message. Depending on the participant's answer to whether or not they have smoked a cigarette and/or E-cigarette in the previous time period, they might receive different combinations of questions. For example, there are 6 questions in the first message each day for the 3 day baseline assessment of cigarette use. However if the participant has not smoked any cigarettes in the previous time period, they will only receive 3 of the questions. Each question is sent to the participant only after the previous one receives a response.

During the intervention stage which will last 3 weeks, we will again send text messages 4 x/day. These messages will assess the following 1) number of cigarettes smoked in the previous time period, 2) use of e-cigarettes, 3) satisfaction with cigarettes and/or e-cigarette ("On a scale of 0-9 how pleasurable was the last [cigarette/E-cigarettes]?"), and 4) cravings ("On a scale from 0-9 how much do you want to smoke a CIGARETTE right now?"). The first text of the day will also ask how soon after waking participants smoked a cigarette and used an e-cigarette and if they used cigarettes, how much do they want to smoke fewer cigarettes than usual and how hard it would be to use E-cigs only. Questions about use of e-cigarettes will include the following: 1) how many separate times in the previous time period did you use your e-cigarette ("time" is defined as around 5 or more puffs or 5 or more minutes of use), 2) On average, how many puffs did you take with each use, and 3) How many minutes ago was your last E-cigarette puff? We will use numerical scales because our experience has demonstrated that this allows for more accurate data collection.

If subjects do not return any messages for a 24 hour period we will contact them by phone to assess if there is a problem with receiving the texts.

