Secondary outcomes: We will assess potential side effects associated with e-cigarette use, additional use of other tobacco products and/or marijuana, satisfaction with the e-cigarettes, nicotine urges/cravings and withdrawal symptoms. An exploratory secondary aim includes assessing differences in the primary and secondary outcomes between the intervention arms.

Name of study: Assessing the use of electronic cigarettes (e-cigarettes) as a harm reduction strategy

Feasibility measures include: 1) Percentage of subjects screened who are eligible and enroll, 2) percentage retained at 3 and 12 weeks, 3) retention across study conditions, 4) consistency in tracking use of e-cigarettes and cigarettes, and 5) satisfaction with e-cigarettes.

Characteristics of the Research Population

Described above under the study participants section.

Number of Subjects

We expect to enroll 100 smokers total, 50 in each arm.

Gender of Subjects

We would ensure equitable inclusion of both men and women in this study.

Age of Subjects

All subjects will be 21-35. We are particularly interested in studying the effectiveness of e-cigarettes as a harm reduction strategy among young adults as this is an understudied population and one that has demonstrated exceptionally high rates of adoption of this product.

Racial and Ethnic Origin

We will recruit across all racial and ethnic groups.

Inclusion Criteria

All subjects must be between 21-35 years old, daily smokers, smoke at least 10 cigarettes per day, interested in reducing CPDs, able to provide consent, use a cell phone, are willing/able to receive and respond to daily text messages regarding their cigarette use and e-cigarette use on their cell phone, and are willing to use an e-cigarette for 3 weeks.

Exclusion Criteria

Subjects will be excluded if they are pregnant and/or breast feeding (self-reported), are currently using smoking cessation medications (including other forms of NRT, bupropion, or varenicline), are enrolled in a smoking cessation program or another cessation trial, have used an e-cigarette in the past 14 days, have used any other tobacco products (pipe, cigar, cigarillos, snuff, chewing tobacco, rolling tobacco, or hookah/shisha) in the past 30 days, score ≥ 7 (men) or ≥ 5 (women) on the Alcohol Use Disorders Identification Test (AUDIT-C), score ≥ 5 on the Drug Abuse Screening Test-10 (DAST), or report having a history of asthma, other airways diseases, or heart disease.

Data Analysis and Data Monitoring

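### Both arms receive an e-cigarette plus counselling, so the trial can estimate the effect of nicotine content but not the stated effect of providing e-cigarettes

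*Combined protocol and SAP*

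**What the plan says.** The PURPOSE OF THE STUDY section names feasibility and then "the effects of providing e-cigarettes (or placebo e-cigarettes) on smoking outcomes". Under Primary research questions, question 2 asks "To what extent do smokers reduce CPD when using e-cigarettes to displace cigarette use", with no comparator, and question 3 asks whether the two arms differ. Aim 3 is "To compare the effect of nicotine e-cigarettes (4.5%) vs placebo e-cigarettes on smoking reduction".

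Study design allocates as follows: "Participants will be randomized to one of the two arms: e-cigarettes with nicotine cartridges or e-cigarettes with placebo cartridges (0mg". The Number of Subjects section adds "We expect to enroll 100 smokers total, 50 in each arm". No arm goes without a device.

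Under Study Procedures, "all participants will receive a 20-30 minute behavioral counseling consultation with a trained tobacco counselor". This comes after three days of tracking and before the e-cigarettes are collected. Everyone is encouraged to cut CPD by half and to replace each dropped cigarette with the device. Interest in reducing CPD is an inclusion criterion. Texts go out four times a day (Text message assessment) and are paid (Payment for Participation).

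The Primary outcome paragraph summarises Aim 3 as the share of participants who have halved CPD by week 3 and does not mention arms. The Secondary outcomes paragraph then describes differences between arms, including on the primary outcome, as an exploratory secondary aim.

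**The concern.** An effect of providing something needs a group that was not provided with it, and this trial has none. Several other reasons for smoking less come with the device in both arms: counselling, a reduction goal, repeated self-monitoring with payment, and selection of people who already want to cut down.

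The number most likely to be reported first is the uncontrolled one, because the primary outcome is a change from baseline and the randomised contrast is labelled exploratory. The Data Analysis section does not warn against reading that change as an effect of the device.

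The risk is sharpest if both arms fall by similar amounts. The BACKGROUND section asks how far any benefit comes from behavioural replacement alone. A large fall in both arms with little difference between them would look like an answer to that question. It would fit an effect of counselling and monitoring just as well.

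**Working it through.** **1. The plan's own figures.** Arms: 50 + 50 = 100. Text days: 3 + 21 = 24. Maximum payment: 3 × 20 + 10 + 24 × 4 + 24 × 1 = 60 + 10 + 96 + 24 = 190 dollars. All three match the text. The protocol gives no alpha, power, expected reduction or dropout, so there is no sample-size calculation to reproduce.

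**2. What differs between the arms.**

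| Component | Nicotine arm | Placebo arm | Section |
|---|---|---|---|
| Selected for interest in reducing | yes | yes | Study participants |
| Counselling before supply | yes | yes | Study Procedures |
| Encouraged to halve CPD | yes | yes | Study Procedures |
| Four paid text prompts a day | yes | yes | Text message assessment; Payment |
| E-cigarette supplied | yes | yes | Study design |
| Nicotine in the cartridge | yes | no | Study design |

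Only the last row differs.

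**3. What can be estimated.** Let pN and pP be the proportions halving CPD at week 3 in the nicotine and placebo arms. Let p0 be the proportion who would do so with everything except a device.

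- Effect of nicotine content: pN − pP. Both terms are observed.
- Effect of providing a nicotine e-cigarette: pN − p0. The second term is never observed.
- Effect of providing a placebo e-cigarette: pP − p0. The second term is never observed.

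The purpose statement names the last two effects. The design delivers the first.

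**4. Illustration (assumed values).** Suppose 40% halve CPD at week 3, pooled over 100 people. The part due to the device is 40 − p0, in percentage points:

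| Assumed p0 | 0% | 10% | 20% | 30% | 40% |
|---|---|---|---|---|---|
| Due to device (points) | 40 | 30 | 20 | 10 | 0 |

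The trial's data would look the same in every column. The 95% interval for 40 out of 100 (Wilson) is 31% to 50%, but it describes the 40% itself and says nothing about attribution.

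**5. What attribution would take.** It would need an arm with counselling and no device. With 50 people in that arm against one device arm of 50 (two-sided 0.05, normal approximation for two proportions), power would be 95% for 10% versus 40%, 59% for 20% versus 40%, and 18% for 30% versus 40%. Against both device arms pooled (100) it would be 99%, 70% and 22%. A third arm would settle the matter only if p0 were low.

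**6. The interval before pick-up.** The 24 text days are used up by 3 of tracking and 21 of product use, so none is allotted between the end of tracking and pick-up. The length of that interval is not stated.

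**The case against.** The strongest reply is that the design suits its real aims. Giving both arms a device is a legitimate way to isolate nicotine in a pilot. Aims 1 to 3 are feasibility, patterns of use, and nicotine versus placebo, and none is a before-and-after effect of the device. Question 2 asks about reduction while using e-cigarettes and can be answered descriptively. No planned analysis credits pooled change to the device, and the parenthesis in the purpose sentence may simply name the two arms. All of this stands, and it is why the remedy is mainly wording. It does not remove the mismatch between a purpose stated as an effect, a primary outcome without a comparator, and an arm contrast labelled exploratory.

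Three stronger readings are tempting, and the documents do not support them.

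- *Texting stops between counselling and pick-up, so an early fall caused by counselling is wrongly credited to the device.* The pause is only inferred from the day count. The interval could be about zero if pick-up is on the same day, and the schedule figure (Figure 2) was not available to check. Any pause would start when tracking ends, before counselling. The count item in Table 2 asks about smoking since the last report, so read literally the first product-period text could take in the interval as one lumped count.
- *A given fraction of the reduction is due to counselling.* The documents give no rate for counselling alone. Any such fraction only restates the assumption put in.
- *Question 2 commits the trial to a causal claim.* It permits one but does not require it.

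**Conclusion.** The point holds as a limit on what may be claimed. Randomisation supports a causal statement about nicotine content only. The e-cigarette's share of a within-arm or pooled reduction is unidentified, from none to all of it (0 to 40 points in the assumed 40% example), taking it that the device does not increase smoking. This rests on features the protocol states outright: a device in both arms, and counselling, goal and monitoring for everyone. It needs no assumption about the interval before pick-up, and a perfect baseline would not remove it.

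Feasibility is untouched. So is the validity of nicotine versus placebo, though its precision is modest: with 50 per arm, power is 59% for an assumed 20% versus 40%. A reader should not infer that the trial is invalid or that a pilot of this size must add an arm.

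**What to change.** 1. Reword the purpose and question 2. The purpose becomes feasibility plus the effect of nicotine content in e-cigarettes given alongside counselling and monitoring. Question 2 is marked as descriptive.
2. In the Data Analysis section, state that change within an arm or pooled is reported as *change under counselling, monitoring and e-cigarette provision*, and not as an effect of e-cigarettes.
3. Make the randomised comparison the estimate of effect for Aim 3, and say so consistently in Study Aims, Primary outcome and Secondary outcomes. Report it with a confidence interval, given the modest precision.
4. Optional: state the interval between the end of tracking and pick-up. If there is one, continue the existing cigarette-count texts through it and report that CPD descriptively only. It cannot separate counselling from device effects at week 3, and participants in that interval already know the device is coming.

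Items 1 to 3 cost nothing beyond editing and a more modest claim. Item 4 costs up to 4 + 1 = 5 dollars per participant per day, or 5 × 100 = 500 dollars per day for the full sample, and nothing if there is no interval.

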Follow-up assessment study visits: At 1 and 3 weeks, we will assess withdrawal symptoms using the Minnesota Nicotine Withdrawal Scale (MNWS), e-cigarette use, cigarette use, quit attempts, and reduction in number of cigarettes used/day. Using Atkinson's treatment satisfaction scale, we will assess side effects associated with using the e-cigarette, convenience of use, perceived effectiveness, and global satisfaction with the product (Atkinson 2004). At the final study visit (week 3) we will also assess changes in baseline readiness to quit, intention to quit, norms related to smoking and using e-cigarettes, confidence in quitting and changes in intention to quit. At 12 weeks post starting e-cigarettes we will conduct follow up telephone surveys to assess current e-cigarette and cigarette use.

At each follow up assessment, RAs will complete a checklist for all of the activities including, completing surveys, and providing e-cigarettes. Note that we will schedule visits up to 4 times. If the subject misses all of those visits he/she will be considered lost to follow up. We will also attempt to contact subjects up to 10 times at different hours of the day and via text message to schedule or reschedule appointment to increase retention rates.

Table 1. In person survey assessments

Measures	Screener	Baseline	Wk 1	Wk 3	Wk 12 telephone
Socio demographics	X				
Smoking history and nicotine dependence		X			
Other tobacco products and marijuana use		X			
Readiness to quit		X		X	

Name of study: Assessing the use of electronic cigarettes (e-cigarettes) as a harm reduction strategy

Importance and confidence in quitting		X	X	
Smoking urges for traditional cigarettes (QSU-Brief)		X	X	
Self-efficacy questionnaire (SEQ12)		X	X	
Secondhand home policy and other smokers at home		X	X	
Risk perception (e-cigarettes)		X		
Social norms		X	X	
History of E-cigarette use		X	X	
Health status		X		
Behavioral dependence scale		X	X	
Current E-cigarettes use		X		
Treatment satisfaction scale (Side effects, Effectiveness, convenience related to e-cigarettes)			X	X
Minnesota Nicotine Withdrawal Scale			X	X
Current cigarette use		X	X	X
1. Someday, every day, not at all				
2. Number per day on days smoke (Self-report and CO and saliva validated abstinence)				
Quit attempt (24 hour) in past week			X	X
Acceptability and Receptivity to txt messages			X	X

Text message assessment:

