Table 2. Text messages and schedule

Rule (based on answer to the first question)	Text	3 days baseline tracking cig use				Intervention period			
		1 st	2 nd	3 rd	4 th	1 st	2 nd	3 rd	4 th
	Since your last report: Did you smoke a cigarette and/or E-cigarette? [no=0; cig=1; Ecig=2; both=3]	X	X	X	X	X	X	X	X
	Thinking about this morning, how many minutes after waking did you smoke your first cigarette? (Text 9999 if you did not smoke any cigarettes today)				X				X
	Thinking about this morning, how many minutes after waking did you use your first E-cig? (Text 9999 if you did not use any E-cigs today)								X
	Thinking about TODAY only: Do you want to smoke fewer cigarettes than usual? [0=Not at all ; 9=Very, Very Much]					X			
	Thinking about TODAY only: How hard would it be to use E-cigs ONLY? [0=Not at all ; 9=Extremely]					X			
If used cig	Since your last report: How many cigarettes did you smoked?	X	X	X	X	X	X	X	X
If used cig	How many minutes ago did you smoke a cigarette? [Text "0" if your are currently smoking]	X	X	X	X	X	X	X	X
If used cig only	On a scale of 0-9 how satisfying was your last cigarette? [0=Not at all – 9=Extremely Satisfying]	X	X	X	X	X	X	X	X
If used e-cig	Since your last report: How many separate times did you use an E-cigarette?					X	X	X	X
If used e-cig only	On average, how many puffs did you take with each use?					X	X	X	X
If used e-cig	How many minutes ago was your last E-cigarette puff? [Text "0" if you are currently using an E-cigarette]					X	X	X	X
If used e-cig	On a scale of 0-9 how satisfying was your last E-cigarette? [0=Not at all – 9=Extremely Satisfying]					X	X	X	X
	On a scale of 0-9, how much do you want to smoke a CIGARETTE right now? [0=Not at all – 9=Very, Very much]	X	X	X	X	X	X	X	X
	Thank you for completing the survey.	X	X	X	X	X	X	X	X

Primary outcome: For Aim 3, the primary outcome will be reduction in CPD and we will summarize this data as the proportion of participants who achieve 50% reduction in CPD at 3 weeks. Smoking reduction will be measured by a combination of self-report, text message data and changes in CO and saliva cotinine between baseline and end of treatment (3 weeks).

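### The listed survey item for cigarettes per day has no count of smoking days, so wherever the survey supplies CPD (above all at week 12) reduction is understated in people who become some-day smokers

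*Combined protocol and SAP*

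**What the plan says.** In Table 1 (In person survey assessments), the row for current cigarette use has two parts. The first is a status with the levels "Someday, every day, not at all". The second is "Number per day on days smoke". A separate row reads "Quit attempt (24 hour) in past week". No listed item asks on how many days the participant smoked.

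The inclusion criteria require a "daily smoker, smokes at least 10 cigarettes a day". The Primary outcome paragraph summarises the result as "the proportion of participants who achieve 50% reduction in CPD at 3 weeks" and adds: "Smoking reduction will be measured by a combination of self-report, text message data and changes in CO and saliva cotinine". It does not say which source supplies CPD, over what window, or how the sources are combined.

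The text messages run for 24 days (3 baseline, 21 intervention), four times a day. Each prompt first asks whether the participant smoked, with a code for no, and then, if so: "Since your last report: How many cigarettes did you smoked".

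Aim 3 compares the arms at 1, 3 and 12 weeks. For the last of these, the section on follow-up visits says: "At 12 weeks post starting e-cigarettes we will conduct follow up telephone surveys to assess current e-cigarette and cigarette use". By then the texts have ended, and CO and saliva cotinine are collected only at baseline and the third study visit.

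**The concern.** A percent reduction is meaningful only if the same quantity is measured before and after. For a daily smoker, the number smoked per smoking day is average CPD. For someone who now smokes on some days, it is average CPD multiplied by 7/d. The status item shows that such a person is a some-day smoker but not how many days that means, so the survey answers cannot be converted back to an average. The quit-attempt row does not fill the gap. As listed, it records an attempt in one week, not a number of smoke-free days.

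The protocol allows for this pattern of smoking. It offers a some-day category, and its text schedule has a code for a day without cigarettes.

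At stake are the size of the reduction and the 50% responder status of anyone who cuts down partly by skipping days. Given accurate answers, the error in an individual runs one way: the item can miss a responder but cannot create one. At week 12 there is no second source to reveal or repair it.

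**Working it through.** The documents give no figure on this point to reproduce, so the check is direct arithmetic.

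**Inputs.** The 50% threshold is from the Primary outcome paragraph. Smoking on 7 of 7 days at baseline follows from the inclusion criteria. The values of B, c and d in the examples are assumptions.

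- B = baseline CPD
- c = cigarettes per smoking day at follow-up, and r = c/B
- d = smoking days per week at follow-up

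**Formulas.**

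- Reduction by the survey item: 1 − r
- Reduction in all-day CPD: 1 − r·d/7
- A true responder is missed when r > 0.5 and r·d/7 ≤ 0.5, that is 0.5 < r ≤ 3.5/d, with r capped at 1 for someone who smokes no more per smoking day than at baseline

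**Range of r in which a responder is missed.**

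| d | 3.5/d | r missed | whole cigarettes, B = 20 |
|---|---|---|---|
| 7 | 0.500 | none | none |
| 6 | 0.583 | above 0.50 to 0.583 | 11 |
| 5 | 0.700 | above 0.50 to 0.70 | 11 to 14 |
| 4 | 0.875 | above 0.50 to 0.875 | 11 to 17 |
| 3 | 1.167 | above 0.50 to 1 | 11 to 20 |

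At the minimum entry level, B = 10, no whole number is missed at d = 6; 6 and 7 are missed at d = 5, and 6 to 8 at d = 4.

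**Worked cases.**

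| B | c | d | all-day CPD = c·d/7 | by the item | all-day |
|---|---|---|---|---|---|
| 15 | 10 | 4 | 40/7 = 5.7 | 33% | 62% |
| 20 | 12 | 5 | 60/7 = 8.6 | 40% | 57% |
| 20 | 11 | 6 | 66/7 = 9.4 | 45% | 53% |
| 20 | 16 | 4 | 64/7 = 9.1 | 20% | 54% |

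Each is a non-responder by the item and a responder by all-day CPD.

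**Who keeps the correct responder status.** Full abstainers do, because their status is not at all and CPD is 0. Every-day smokers do, because d = 7. So do those with r ≤ 0.5, although the size of their reduction is still understated if d < 7.

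**Effect on the arm comparison.** With true responder rates p1 and p2, and fractions m1 and m2 of responders missed, the observed difference is p1(1 − m1) − p2(1 − m2). Assume p1 = 50% and p2 = 30%, a true difference of 20 points:

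- m1 = m2 = 20%: 40% − 24% = 16 points
- m1 = 30%, m2 = 10%: 35% − 27% = 8 points
- m1 = 0, m2 = 20%: 50% − 24% = 26 points

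Equal losses shrink the difference in proportion, and greater loss in the nicotine arm shrinks it further. If the loss falls mainly on placebo, the difference can widen. The documents give neither the rates nor the fractions.

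**The case against.** A reader might infer that participants with smoke-free days will be misclassified in the week-3 primary outcome. The documents do not support that. No passage scores responders on the survey item alone. The text counts run through the 21 intervention days and accept a reply of no smoking, so a source that includes zero days already exists for week 3. This objection stands. What remains at week 3 is that the protocol names several sources without saying which one is CPD, and that texts show smoke-free days only when they are answered.

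A reader might also infer a bias toward no difference between the arms. That depends on how the missed responders are distributed, which is unknown, and the protocol calls the assessment of arm differences exploratory.

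Other objections have some force. Table 1 is a summary and the questionnaire is not in the documents, so a days-smoked question may exist there. The prose for weeks 1 and 3 also lists reduction in daily number as a measure. The columns of Table 1 are broken in the available text, so it cannot be confirmed that the week-12 call uses the same wording. The counselling strategies mostly concern particular cigarettes within a day, so smoke-free days may be uncommon, and with one such day a week the affected band is narrow (r from 0.50 to 0.583). These points limit the certainty and the likely size. They do not supply a count of smoking days at week 12.

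**Conclusion.** The concern holds in a conditional form. Wherever the survey item supplies CPD, a participant who moves from daily to some-day smoking has the reduction understated, and is missed as a 50% responder if 0.5 < r ≤ 3.5/d. The clearest exposure is week 12, an Aim 3 time point at which the telephone survey is the only source, on the assumption that the call uses the wording in Table 1. Week 3 is exposed only if the survey item is used in place of the text counts, a choice that the protocol leaves open.

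For an individual the gap can be large (33% against 62% in the first worked case). The number of participants affected, and so the effect on any responder rate or arm difference, cannot be estimated from the documents. The change is worth making because the error runs in one direction, is nearly free to prevent, and cannot be repaired once week-12 data are collected.

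**What to change.** 1. In the week 1, week 3 and week 12 surveys, ask on how many of the past 7 days the participant smoked. Baseline needs no such question, since entrants smoke daily.
2. Define survey CPD as (days smoked × number per day on those days)/7, with a status of not at all set to 0. Use it for percent reduction and responder status at week 12.
3. For the week-3 primary outcome, define CPD over all days in a fixed window, zero days included. Name the text counts as the CPD source and the all-day survey CPD as the back-up when texts are missing, and state in advance when they count as missing. Survey recall should not replace the text counts.

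The cost is one short question per contact and a few lines of definition. No extra visit is needed.
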